**Table 3 Imaging and Treatment After 1st Radiologic Evidence of PD**

	Clinically Stable		Clinically Unstable	
	Imaging	Treatment	Imaging	Treatment
1st radiologic evidence of PD	Repeat imaging at $\geq 4$ weeks at site to confirm PD	May continue study treatment at the investigator's discretion while awaiting confirmatory scan by site	Repeat imaging at $\geq 4$ weeks to confirm PD per physician discretion only	Discontinue treatment
Subsequent scan confirms PD	No additional imaging required	Discontinue treatment	No additional imaging required	N/A
Subsequent scan shows SD, PR, or CR	Continue regularly scheduled imaging assessments	Continue study treatment at the investigator's discretion	Continue regularly scheduled imaging assessments	May restart study treatment if condition has improved and/or is clinically stable per investigator's discretion

CR = complete response, N/A = not applicable, PD = progressive disease, PR = partial response.

Subjects going off study without disease progression will also undergo tumor assessments every 6 weeks until disease progression is documented or another anticancer therapy is initiated.

irRECIST guidelines are described in [Appendix 1](#).

Tumor assessments per modified RECIST 1.1 will follow Eisenhauer et al. (2009), however, up to 10 target lesions, up to 5 per organ, may be selected (as opposed to a maximum of 5 target lesions, up to 2 per organ).

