irPD	
Minimum 20% increase and a minimum 5 mm absolute increase in SOD compared to nadir, or irPD for non-target lesion(s) or unequivocal new lesion(s).
 
 
• Confirmation of progression is recommended at a minimum of 4 weeks after the first irPD assessment (preferably at next tumor assessment timepoint).
 
 
The decision to continue study treatment after the first evidence of PD is at the Investigator's discretion based on the clinical status of the subject as described in table below.
 
  
 	Clinically Stable	Clinically Unstable	
 
 Imaging	Treatment	Imaging	Treatment	
   
 1st radiologic evidence of PD	Repeat imaging at <math>\geq 4</math> weeks (next TA timepoint) to confirm PD	May continue study treatment at the Investigator's discretion while awaiting confirmatory scans	Repeat imaging at <math>\geq 4</math> weeks to confirm PD per physician discretion only	Discontinue treatment	
 
 Subsequent scan confirms PD	No additional imaging required	Discontinue treatment	No additional imaging required	N/A	
 
 Subsequent scan shows SD, PR or CR	Continue regularly scheduled imaging assessments	Continue study treatment at the Investigator's discretion	Continue regularly scheduled imaging assessments	May restart study treatment if condition has improved and/or clinically stable per Investigator's discretion	
  
 
Subjects may continue receiving study treatment while waiting for confirmation of irPD if they are clinically stable as defined by the following criteria:
 
 
• Absence of signs and symptoms (including worsening of laboratory values) indicating disease progression
 
• No decline in ECOG performance status
 
• Absence of rapid progression of disease
 
• Absence of progressive tumor at critical anatomical sites (e.g., cord compression) requiring urgent alternative medical intervention
 
		Clinically Stable		Clinically Unstable		Imaging	Treatment	Imaging	Treatment	1 st radiologic evidence of PD	Repeat imaging at $\geq 4$ weeks (next TA timepoint) to confirm PD	May continue study treatment at the Investigator's discretion while awaiting confirmatory scans	Repeat imaging at $\geq 4$ weeks to confirm PD per physician discretion only	Discontinue treatment	Subsequent scan confirms PD	No additional imaging required	Discontinue treatment	No additional imaging required	N/A	Subsequent scan shows SD, PR or CR	Continue regularly scheduled imaging assessments	Continue study treatment at the Investigator's discretion	Continue regularly scheduled imaging assessments	May restart study treatment if condition has improved and/or clinically stable per Investigator's discretion

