	Clinically Stable		Clinically Unstable																						
	Imaging	Treatment	Imaging	Treatment																					
1 st radiologic evidence of PD	Repeat imaging at $\geq 4$ weeks (next TA timepoint) to confirm PD	May continue study treatment at the Investigator's discretion while awaiting confirmatory scans	Repeat imaging at $\geq 4$ weeks to confirm PD per physician discretion only	Discontinue treatment																					
Subsequent scan confirms PD	No additional imaging required	Discontinue treatment	No additional imaging required	N/A																					
Subsequent scan shows SD, PR or CR	Continue regularly scheduled imaging assessments	Continue study treatment at the Investigator's discretion	Continue regularly scheduled imaging assessments	May restart study treatment if condition has improved and/or clinically stable per Investigator's discretion																					

	If irPD is confirmed and the subject is experiencing extraordinary clinical benefit, site must contact Sponsor to discuss continuing treatment
irNE	Used in exceptional cases where insufficient data exists due to poor quality of scans or missed scans or procedure

Derivation of irRECIST overall responses			
Measurable response	Nonmeasureable response		
Target Lesions (% change in SOD)*	Non-Target Lesions Status	New Lesions Status	Overall Response (irRECIST)
↓100	Absent	Absent	irCR ¥
↓100	Present/NE	Absent	irPR ¥
↓≥30	Present/Absent/NE	Absent	irPR ¥
↓<30 to <20↑	Present/Absent/NE	Absent	irSD
↓100 ↓≥30 ↓<30 to <20↑ NE	Present/Absent/NE	Present	irPD ¥
↓100 ↓≥30 ↓<30 to <20↑ NE	Unequivocal progression	Any	irPD ¥
↑≥20 from nadir	Any	Any	irPD ¥
NE	Present/Absent/NE	Absent	irNE ¥

\* Decreases assessed relative to baseline, including measureable lesions only.

¥ Assuming response (irCR) and progression (irPD) are confirmed by a second, consecutive assessment at least 4 wk apart.

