5.4.1 Efficacy Analyses According to immune-related RECIST (irRECIST)

Tumor assessments and overall response to the treatment according to irRECIST are presented in Section 13.2. The confirmation of progressive disease (irPD) is required at least 4 weeks after the initial irPD. If irPD at two consecutive tumor assessment visits with less than 4 weeks, the additional confirmation of irPD visit is required. If irPD is confirmed, the documented start date of irPD is determined as follows:

1. The date of the initial irPD if it is confirmed on consecutive tumor assessment visits.
2. The date of the second irPD if the initial irPD is confirmed not on consecutive tumor assessment visits.

The best overall response (BOR) is defined as follows:

- **irCR**

To achieve BOR of irCR, irCR must be observed at two consecutive tumor assessment visits with at least 4 weeks apart before the confirmed irPD, death, or end of study (whichever occurs first). If complete response at two consecutive tumor assessment visits with less than 4 weeks, the confirmation of irCR at the next assessment visit is required. The documented start date of irCR is defined as the date of the initial irCR.

- **irPR**

When BOR of irCR is not achieved, BOR of irPR can be achieved by that an initial irPR is confirmed by irPR or irCR at next consecutive visit (≥ 4 weeks after the first irPR response). If irPR or irCR happens at two consecutive tumor assessment visits within 4 weeks, the additional confirmation of irPR (irPR or irCR in a later visit) is needed for BOR of irPR. The documented start date of irPR is the date of the initial irPR.

- **irSD**

If the documented start date of irPD is not the first evaluable tumor assessment visit after the first dose of study drug and the BOR is not a confirmed irCR/irPR, then the BOR is stable disease (irSD) when the duration of irSD is no less than 5 weeks. The duration of irSD is defined as the time from the first dose date to the documented start date of irPD, death, or the last evaluable tumor assessment (whichever occurs first).

- **irPD**

If the documented start date of irPD is the first evaluable tumor assessment visit after the first dose of study drug, then the BOR is irPD.

Table 1 listed general rules in the derivation of BOR with two consecutive tumor response results.

Table 1 Derivation of BOR with Two Consecutive Tumor Response Results

| Timepoint 1 Initial Response | Timepoint 2 Follow-up Response ≥ 4 weeks | BOR |

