|---------------------------------|--|--|
| irCR | irCR | irCR |
| irCR | irPR/irSD/irPD | irSD/irPR* |
| irPR | irPR/irCR | irPR |
| irPR | irSD | irSD |
| irPR | irPD | irSD |
| irSD | irSD | irSD |
| irSD | irPD | irSD, provided minimum irSD duration met |
| irPD | irPD | irPD |

*If an irCR is truly met at first time point, then any disease seen at a subsequent time point, even disease meeting irPR criteria relative to baseline, makes the disease irPD at that point (since disease must have reappeared after irCR). Best response would be irSD. However, sometimes 'irCR' may be claimed when subsequent scans suggest small lesions were likely still present and in fact the patient had irPR, not irCR at the first time point. Under these circumstances, the original irCR should be changed to irPR and the best response is irPR.

- **irNE**

The BOR will be irNE in the following scenarios:

- No evaluable tumor assessment
- Only one evaluable tumor assessment with the result of either irPD or irCR/irPR/irSD but the duration of irSD is less than 5 weeks.

- **Handling of Missing /Not Evaluable Tumor Assessments**

The following rules will be used to handle missing and/or not evaluable tumor assessments:

- One missing or not evaluable tumor assessment will be ignored if it is between two evaluable tumor assessments.
- All the missing and/or not evaluable tumor assessments will be ignored if they are the only ones in between two irPDs. In this case, the irPD is confirmed and the documented start date of irPD is the date of the first irPD.
- All the missing and/or not evaluable tumor assessments will be ignored if there is no evaluable tumor assessment after them.
- Two irCRs, two irPR, or irPR and irCR with two or more missing and/or not evaluable tumor assessments in between will result in not evaluable result, i.e., irNE.

Objective Response Rate (ORR)

The objective response rate (ORR) is the proportion of patients achieving a best overall response of confirmed irPR or irCR according to irRECIST from first dose date until disease progression, death, or end of study (whichever occurs first). Subjects who do not have a tumor response assessment for any reason will be considered nonresponders and will be included in the denominator when calculating the response rate. The count and percentage for the ORR will be summarized by dose group.

Time to Response (TTR)

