The time to response (TTR) is defined as the elapsed time (weeks) from the first dose date to the documented start date of confirmed irCR/irPR according to irRECIST. The descriptive statistics for the TTR will be summarized by dose group for the patients with the BOR of confirmed irCR/irPR.

Duration of Response (DOR)

The duration of response (DOR) is defined as the time (months) from the documented start date of confirmed irCR/irPR according to irRECIST until the documented start date of irPD or death (whichever occurs first).

For subjects with the BOR of irCR/irPR who did not die and had no documented progression before the cut-off date for the end of the study, or before early discontinuation (including discontinuations due to toxicity, undocumented clinical progression, change of cancer treatment, or decreasing performance status), and who died or progressed after more than one missed visit, will be censored on the date of their last assessment with the BOR of irCR, irPR or irSD.

The descriptive statistics (median and its standard error, Q1 and Q3) for the DOR will be summarized by dose group for the patients with the BOR of confirmed irCR/irPR using Kaplan-Meier method.

Progression-Free Survival (PFS)

Progression-free survival is defined as alive without confirmed irPD using irRECIST at the end of study or certain evaluation time points such as 3 months, 6 months, etc. The time for PFS is defined as the elapsed time from first dose date to the documented start date of irPD or death (whichever occurs first).

In analysis of PFS, the censoring rule is as follows:

- Subjects who did not die and had no documented progression (confirmed irPD) before the cut-off date for the end of the study, or before early discontinuation (including discontinuations due to toxicity, undocumented clinical progression, change of cancer treatment, or decreasing performance status), PFS will be censored on the date of their last evaluable assessment.
- Subjects who died or progressed after more than one missed visit, or non-evaluable assessment, or a combination of two, PFS will be censored on the date of their last evaluable assessment before the death or progression.

The rate for PFS will be summarized by evaluation time point and dose group. The time curve and median of PFS will be estimated and reported by the Kaplan-Meier method.

Disease Control Rate (DCR)

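### SAP 5.4.1 has no proper place for unconfirmed irPD: a sole progression scan becomes irNE, two close ones default to irSD, and a living subject who stops for progression is censored for PFS

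*SAP*

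**What the plan says.** **When a repeat scan is required.** Protocol Table 3, repeated in Protocol Appendix 1 and SAP 13.2, stops treatment at the first radiologic progression in a clinically unstable subject. Its imaging cell ends "weeks to confirm PD per physician discretion only". The text of Protocol 9.5.2 above the table describes a repeat assessment after irPD without that exception, so the two need reconciling. On irPD, Appendix 1 says "Confirmation of progression is recommended at a minimum of 4 weeks after the first irPD assessment".

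**What the analysis needs.** SAP 5.4.1 says "The confirmation of progressive disease (irPD) is required at least 4 weeks after the initial irPD". For close scans it adds "If irPD at two consecutive tumor assessment visits with less than 4 weeks, the additional confirmation of irPD visit is required". A documented irPD start date is given only once irPD is confirmed. BOR irPD depends on that date: if it "is the first evaluable tumor assessment visit after the first dose of study drug, then the BOR is irPD".

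**irNE.** Appendix 1 describes irNE as "Used in exceptional cases where insufficient data exists due to poor quality of scans or missed scans or procedure". SAP 5.4.1 adds a different scenario: "Only one evaluable tumor assessment with the result of either irPD or irCR/irPR/irSD but the duration of irSD is less than 5 weeks".

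**irSD.** In SAP 5.4.1 this is a residual class. It applies when there is no confirmed response, the irPD start date is not at the first evaluable scan, and the duration is at least 5 weeks. Duration runs to the irPD start date, death or the last evaluable scan, whichever is first. DCR counts these subjects.

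**PFS.** The first SAP censoring rule covers subjects who did not die and had no confirmed irPD before cut-off or early discontinuation, and names undocumented clinical progression and falling performance status among the reasons. They are censored at the last evaluable scan. The second rule censors "Subjects who died or progressed after more than one missed visit". Protocol 9.7.1.7 instead treats subjects who withdraw because of progressive disease as having progressed. SAP Section 7 says that no planned analysis was changed.

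**The concern.** The protocol accepts that some progressing subjects will never have a confirming scan, and these are the clinically unstable ones. The SAP makes the confirming scan a condition for recording progression at all, and says nothing specific about subjects who lack it. They are then sorted by rules written for other situations.

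At stake are the BOR table, DCR and PFS under irRECIST, the secondary efficacy criteria. Results are tabulated by dose group, mostly of 6 subjects, and Protocol 9.1.1.4 lists evidence of clinical activity among the considerations for choosing the RP2D. One misclassified subject is visible at that size. Censoring a subject for PFS because he or she became too unwell to be rescanned is also informative censoring.

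**Working it through.** No figure in the documents depends on this point, so there is none to reproduce. The check applies the SAP 5.4.1 rules literally to scan sequences.

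**Timing inputs.** Scans fall in the 6th week and every 6 weeks after that (Protocol 9.5.2), earlier if clinically indicated. A scan on Day 36 to 42 is (36 − 1)/7 = 5.0 to (42 − 1)/7 = 5.9 weeks after first dose. The 5-week irSD minimum therefore does not screen out a first scheduled scan.

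**BOR by sequence (all evaluable post-baseline scans shown)**

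| Scans | Interval | irPD start date? | BOR under SAP 5.4.1 |
|---|---|---|---|
| irPD Week 6 only | none | no | irNE |
| irPD Week 4 only | none | no | irNE |
| irPD Weeks 4 and 6 | 2 weeks | no | irSD by default |
| irPD Weeks 6 and 9 | 3 weeks | no | irSD by default |
| irPD Weeks 2 and 4 | 2 weeks | no | no class fits (under 5 weeks) |
| irPD Weeks 6 and 12 | 6 weeks | yes, Week 6 | irPD |

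Without the confirmation requirement, as in modified RECIST 1.1 (SAP 5.4.2), all six are PD.

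**Why the close pairs reach irSD.** The irNE scenario needs a single evaluable scan. SAP Table 1 covers only intervals of at least 4 weeks. No start date exists, so none falls at the first scan. The irSD rule must also cover subjects who never progress, so a missing start date cannot exclude a subject from it. Duration then runs to the last evaluable scan, although that scan shows irPD.

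**An ambiguity in the irNE line.** If its 5-week limit is read as applying to irPD too, a sole irPD in the 6th week is not irNE and falls to irSD.

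**PFS, one irPD scan at Week 6, treatment stopped**

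- Alive, no further scan: censored at Week 6 under the first rule.
- Death at Week 9, 14 or 20: 0, 1 or 2 scheduled scan dates have passed (Weeks 12 and 18). Under the second rule only the Week 20 death could be censored, and only if scans that were not required count as missed.

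**Size**

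- Each close-pair case changes DCR by 1/6 = 16.7 points in a cohort of 6, or 1/16 = 6.25 points in an expansion of 16, if all are response-evaluable.
- Illustration with assumed rates: N = 16, 10% to 30% (2, 3 or 5 subjects) unstable with unconfirmed irPD at Week 6, and the rest with confirmed irPD about equally at Weeks 6, 12 and 24. Confirmed irPD at Week 6 is then 4, 4 or 3 subjects.
  - BOR irPD count: 4, 4, 3 under the SAP, against 4 + 2 = 6, 4 + 3 = 7, 3 + 5 = 8 if the unconfirmed irPDs count.
  - Kaplan–Meier PFS just before Week 12, S = 1 − events/16: 12/16 = 0.75, 12/16 = 0.75, 13/16 = 0.81 under the SAP, against 10/16 = 0.63, 9/16 = 0.56, 8/16 = 0.50.

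**The case against.** **Confirmation is in the protocol too.** Protocol 9.7.1.1 defines PFS and DOR by confirmed progression, and the footnote to the Appendix 1 response table assumes a second assessment at least 4 weeks later. This stands. The SAP did not invent the requirement, and the protocol's own wording must be aligned as part of any change.

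**The irNE route moves no rate endpoint.** irNE is neither response nor disease control, and the subject stays in the Response Evaluable Set. This stands: only the irPD and irNE rows of the BOR table change.

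**The irSD route is rare.** It needs an unscheduled scan, and the SAP asks for a further visit when scans are close. This stands as to frequency, but the SAP gives no class when that visit never happens.

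**Later deaths.** A reader might infer that deaths after an unconfirmed irPD are also lost from PFS. The documents do not establish this. Missed visit is undefined. Six-weekly scans continue only for subjects who stop without progression (Protocol 9.1.3.3 and the text under Table 3), so a scan that was never due is not clearly missed. The first censoring rule covers subjects who did not die, and the PFS definition counts death as an event.

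**The protocol's withdrawal rule** speaks of leaving the study, while Table 3 concerns stopping treatment, and the SAP's early discontinuation does not say which it means. This narrows the contradiction but does not remove it.

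**Other analyses show the events.** Modified RECIST 1.1 needs no confirmation of PD, and OS counts every death. True, but both are exploratory.

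**Conclusion.** The point holds in a limited form. On the text as written, a sole irPD scan becomes irNE, contrary to the Appendix 1 meaning. Two irPD scans under 4 weeks apart, the last at 5 weeks or later, default to irSD and count in DCR. A living subject who stops for progression without confirmation is censored for PFS at the scan that showed it, at odds with Protocol 9.7.1.7 and with SAP Section 7.

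A reader might conclude that the rules always favour the drug, or that the fastest progressors vanish from the results. Neither is supported. ORR is unaffected, and DCR moves only on the uncommon irSD route. A subject with irSD at Week 6 and unconfirmed irPD at Week 12 is properly irSD under Table 1.

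The certain size is per subject: one subject in the irPD share and, on the irSD route, 16.7 DCR points in a cohort of 6. The PFS differences above rest on assumed frequencies. Efficacy is secondary and descriptive here, but the change is worth making before database lock because small dose groups inform the RP2D.

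**What to change.** Amend SAP 5.4.1 as follows:

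- **(a) BOR irPD.** Assign it when every evaluable post-baseline scan is irPD and no later evaluable scan exists, dated at the first irPD. Leave Table 1 (irSD then irPD gives irSD) and confirmed responses unchanged. Keep irNE for the Appendix 1 meaning.
- **(b) BOR irSD.** Require at least one time-point result of irSD or better.
- **(c) PFS.** Reconcile the censoring rules with Protocol 9.7.1.7 and 9.7.1.1, so that a subject who discontinues for progressive disease after an irPD scan, with no later evaluable scan, is an event whether or not he or she later dies. State the event date. Define missed visit, and say that scans not required after such an irPD are not missed.
- **(d) Sensitivity analysis.** Report BOR, DCR and PFS with strictly confirmed irPD alongside.

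The irPD rule must not reach subjects with earlier irSD or a confirmed response, and PFS event status must not depend on whether the subject later dies.

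Cost: SAP wording and programming, plus alignment of the confirmed-progression wording in Protocol 9.7.1.1. No scan is added and no treatment rule changes. PFS, DCR and the irPD share may look slightly less favourable.

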- r. Tumor assessments will be performed based on irRECIST and RECIST1.1. Treatment decisions will be based on irRECIST. Tumor assessments will be carried out during the Pretreatment Phase and then every 6 weeks (during the 6th week; counting from C1D1) during treatment cycles in both the Treatment Phase and the Extension Phase. CT scans (with oral and intravenous contrast) of chest, abdomen, and pelvis and of other known sites of disease will be obtained at Screening (within 28 days prior to Cycle 1/ Day 1), using the above tumor assessment schedule, and as indicated clinically. Skin lesions may only be considered as non-index lesions (no photographs required) or as new lesions to add to the tumor burden sum. Subjects with SCCHN must also have head and neck scans performed at all tumor assessment timepoints. MRI scans may be used instead of CT scans for (head, neck) abdomen and pelvis; however, chest must be assessed using CT. Chest disease may not be followed using chest x-ray. CT scans should be performed with oral and iodinated IV contrast and MRI scans with IV gadolinium chelate unless there is a medical contraindication to contrast. If iodinated IV contrast is contraindicated, chest CT should be performed without IV contrast. The same method of assessment must be used at all time points as used at Screening.
- s. Screening brain scans will be performed by MRI pre- and post- gadolinium or CT with contrast within 4 weeks prior to C1D1. During the Treatment Phase, CT/MRI of the brain will be performed if clinically indicated, and within a target of 1 week after a subject achieves a irCR. For subjects with history of treated brain metastases, brain scans will be performed at every tumor assessment time point. The same methodology and scan acquisition techniques used at screening should be used throughout the study to ensure comparability.

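### SAP 5.4.1 scores two responses separated by two missed scans as irNE, against its own irSD rule, so read literally a subject still in response drops out of DCR

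*SAP*

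**What the plan says.** SAP 5.4.1 defines BOR category by category and then adds rules for missing or non-evaluable scans.

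- **Gap between responses.** Two irCRs, two irPRs, or one of each "with two or more missing and/or not evaluable tumor assessments in between will result in not evaluable result, i.e., irNE".
- **Single gap.** "One missing or not evaluable tumor assessment will be ignored if it is between two evaluable tumor assessments".
- **Trailing gaps.** Missing scans are "ignored if there is no evaluable tumor assessment after them".
- **Gap between progressions.** "All the missing and/or not evaluable tumor assessments will be ignored if they are the only ones in between two irPDs"; irPD then counts as confirmed.
- **irSD.** If irPD does not start at the first evaluable visit and no response is confirmed, "then the BOR is stable disease (irSD) when the duration of irSD is no less than 5 weeks". Duration runs from first dose to "the documented start date of irPD, death, or the last evaluable tumor assessment (whichever occurs first").
- **irNE list.** Two scenarios are given: no evaluable assessment at all, or "Only one evaluable tumor assessment with the result of either irPD or irCR/irPR/irSD but the duration of irSD is less than 5 weeks".

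Scans are taken "every 6 weeks (during the 6th week; counting from C1D1") per the schedule in SAP 13.1. SAP 5.4.1 counts in DCR a BOR of confirmed irCR, confirmed irPR, or irSD of at least 5 weeks. For CBR the irSD threshold is 24 weeks. irNE counts in neither. SAP 5.4 runs all efficacy analyses on the Response Evaluable Set.

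**The concern.** Two rules in one section apply to the same scan record and give different BORs, with no order of precedence. If the missing-scan rule is taken at its word, the ordering of outcomes is perverse: a second scan showing continued response removes from DCR a subject who would have been counted without that scan, or with a worse result on it.

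DCR is a secondary endpoint reported by dose group, and the groups are small. The affected subject has post-baseline evaluations, so stays in the Response Evaluable Set denominator and counts as a failure rather than being set aside. Two programmers could also derive different BORs from the same data, and the choice might then be made after the results are known.

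**Working it through.** There is no stated figure to reproduce, because the point concerns a derivation rule. The check applies the SAP 5.4.1 rules to scan patterns on the 6-weekly schedule.

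**Durations.** A scan in week w falls on study days 7(w − 1) + 1 to 7w. Duration in weeks is (day − 1)/7 as a date difference, or day/7 if both end days are counted. SAP 5.4.1 does not say which. The ranges below run from the shortest to the longest value across both conventions.

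- Week 6: days 36–42, so 35/7 = 5.0 to 42/7 = 6.0 weeks. The 5-week minimum is met on every scheduled day.
- Week 24: days 162–168, so 161/7 = 23.0 to 168/7 = 24.0 weeks.
- Week 30: days 204–210, so 203/7 = 29.0 to 210/7 = 30.0 weeks.

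**BOR by pattern** (no death, no other evaluable scans):

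| Scan record | BOR, gap rule literal | BOR, irSD rule applied | In DCR |
|---|---|---|---|
| irPR W6, nothing after | irSD | irSD | yes |
| irPR W6, W12 and W18 missed, irSD W24 | irSD | irSD | yes |
| irPR W6, W12 and W18 missed, irPD W24 | irSD | irSD | yes |
| irPR W6, W12 missed, irPR W18 | irPR | irPR | yes |
| irPR W6, W12 and W18 missed, irPR W24 | **irNE** | **irSD** | **no** if literal, **yes** under the irSD rule |

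The first row uses the trailing-gap rule and the fourth the single-gap rule. In the second and third rows no gap rule applies, so the irSD rule decides. SAP Table 1 likewise gives irSD for irPR followed by irSD or by irPD. Among the four records that begin with irPR at Week 6 and have no scan at Weeks 12 and 18, only the one still in response at Week 24 is dropped.

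**Size per affected subject in DCR:**

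- Escalation cohort of 6, all evaluable: 1/6 = 16.7 points.
- Expansion of 16, summarised separately: 1/16 = 6.25, or 6.3 points.
- Expansion of 16 pooled with the 6 escalation subjects at that dose: 1/22 = 4.5 points.

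**CBR.** In the Week 24 example the irSD rule gives 23.0–24.0 weeks. That reaches 24 weeks only for a Day 168 scan with both end days counted. A longer pattern does show a CBR effect: irSD Week 6, irPR Week 12, Weeks 18 and 24 missed, irPR Week 30. The irSD rule gives 29.0–30.0 weeks, which counts in CBR; the literal gap rule gives irNE, which does not.

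**ORR.** In the Week 6 and Week 24 example the response is unconfirmed on either reading, so ORR is the same. Adding irPR at Week 30 changes that. Weeks 24 and 30 are consecutive and at least 4 weeks apart, so the irPR rule confirms the response. A literal gap rule could still be read as imposing irNE because of the earlier Week 6 and Week 24 pair.

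**The case against.** The strongest reply is that the gap rule speaks of a not evaluable result and does not say that BOR is irNE. It can be read as meaning only that this pair fails to confirm a response. The irSD rule would then still apply and nothing would be lost from DCR. The omission of the case from the irNE scenario list favours that reading. This stands as a possible reading, so a reader who infers an established downward bias in DCR goes further than the text allows. But irNE is a named BOR category and the rule sits inside the BOR derivation, so the literal reading is at least as natural. The SAP does not choose between them.

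Three other inferences are tempting and not supported:

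- **That the Week 24 subject also loses CBR because of this rule.** Under the irSD rule that subject generally falls short of 24 weeks anyway, and the Week 6-only subject is not in CBR either.
- **That ORR is safe.** It is safe only if the gap rule does not override a later confirming pair, which the text leaves open.
- **That treating irPD differently is an error.** Accepting progression across any gap while requiring tighter confirmation of response is conservative in both directions, since neither overstates activity. It is a defensible choice and not part of this point.

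The pattern is also narrow. It needs a response, at least two consecutive missed or non-evaluable scans, then another response with no other confirming pair. On the 6-weekly schedule the second response comes no earlier than Week 24. Protocol 9.7.1 sets the final cutoff at 6 cycles for the last enrolled subject (6 × 21 = 126 days, or 18 weeks), so late entrants may never reach it. DCR is descriptive, and the primary objectives are safety and MTD/RP2D.

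**Conclusion.** The conflict is real and should be corrected. On the literal reading, SAP 5.4.1 gives irNE to a subject in response at Weeks 6 and 24 and excludes that subject from DCR, while counting subjects with less evidence of disease control or with a worse Week 24 result. The irSD rule would count all of them.

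The size is 16.7, 6.3 or 4.5 DCR points per affected subject, depending on the group summarised. These figures assume that every subject in the group is in the Response Evaluable Set and that the literal reading is programmed. They are effects per subject, not an expected bias: the documents give no rate for the pattern, and it is probably uncommon. CBR is affected only where irSD reaches 24 weeks, as in the Week 30 pattern. The primary endpoints are not touched.

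**What to change.** Replace the fourth missing-assessment rule in SAP 5.4.1 with wording such as:

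*A pair of responses (two irCRs, two irPRs, or one of each) separated by at least two missing or non-evaluable assessments does not by itself confirm a response. Unless another qualifying pair of assessments confirms one, BOR is derived by the irSD rule: irSD if the duration is 5 weeks or more, otherwise irNE.*

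The condition about another qualifying pair is needed. Without it the sentence could set irSD for a subject whose response is confirmed elsewhere, for example at Weeks 24 and 30, and remove a true responder from ORR. The closing irNE branch will hardly ever apply, since a second response after two missed 6-weekly scans is well past 5 weeks, but it keeps the rule complete.

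The cost is one rule in the SAP and a matching line of derivation code, made before database lock. No data collection changes, and no unconfirmed response becomes confirmed.
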